# Protocol Amendment 3, Summary of Changes

# Amendment 3, 02-May-2023

This amendment is considered to be substantial based on the criteria set forth in Article 10(a) of Directive 2001/20/EC of the European Parliament and the Council of the European Union.

## **Overall Rationale for the Amendment:**

As the duration of this study will extend beyond January 2025, the protocol was updated to prepare for compliance with EU Clinical Trial Regulation 536/2014 (EU-CTR). The protocol has been harmonized across country-specific versions in the EU Member States, to the extent possible. Where not feasible, country-specific requirements are now located in Section 10.5. Additionally, the protocol has been updated to correct inconsistencies among the 3 study cohorts. Additional updates and clarifications were also included. A summary of all changes follows in the table below.

Description of Change	Brief Rationale	Affected	1 Sections
Re-instate close monitoring rules for DILI	Close monitoring rules were initially added to address HPRA concerns. These rules will now apply across all countries.	7.1.1.2 I N	Drug-Induced Liver Injury Monitoring
Study stopping rules were added	Study stopping rules were initially added to address HPRA concerns. These rules will now apply across all countries.	7.1.2 S	Study Stopping Rules
Stopping rules were updated and guidance on electrocardiogram findings are provided	To include electrocardiogram findings as judges by the investigator as a stopping rule for individual participants	7.1.1 S F 10.5 E	Stopping Rules for Individual Participants Electrocardiogram Findings
Added PFTs to the schedule of events	To harmonize schedule of activities with the US version of the protocol	1.3 S	Schedule of Activities

Made changes to the timing of collection of serum AFP, urinalysis, anti-drug antibodies, and blood biomarkers in Cohort 1 SoA	To harmonize schedule of activities between cohorts	1.3	Schedule of Activities
Made changes to the timing of collection of anti-drug antibodies, injection site inspection, hematology, chemistry, and coagulation, DLCO and spirometry, pregnancy test for WOCBP, weight, and serum and CRP in Cohort 2 SoA	To harmonize schedule of activities between cohorts	1.3	Schedule of Activities
Made changes to the timing of collection of urinalysis, anti-drug antibodies, SRGQ, and CLDQ, and added complement collection to Cohort 3 SoA	To harmonize schedule of activities between cohorts	1.3	Schedule of Activities
Specified the duration in which WOCBP must use contraception for at least 12 weeks after last dose of study drug	Was not clearly defined in previous versions	5.1 10.4	Inclusion Criteria Contraceptive Guidance and Collection of Pregnancy Information
Clarified the definition of "pulmonary exacerbation"	To ensure consistency of reporting of exacerbations between sites	8.2.6	Other Pulmonary Information

# 1. **PROTOCOL SUMMARY**

# 1.1. Synopsis

# Protocol Title: A Phase 2, Randomized, Double-blind, Placebo-controlled Study Investigating Safety, Tolerability, Pharmacokinetics and Pharmacodynamics of Two Dose Levels of Belcesiran in Patients with Alpha-1 Antitrypsin -Associated Liver Disease

## Short Title: A Phase 2 Study of Belcesiran in Patients with AATLD

## **Rationale:**

Alpha-1 antitrypsin deficiency (AATD) is caused by inherited autosomal mutations in *SERPINA1*, the gene that encodes the alpha-1 antitrypsin (AAT) protein. The resultant mutant AAT protein (Z-AAT) is prone to misfolding and aggregation as homopolymers in hepatocytes. In individuals homozygous for the autosomal mutant AAT Z-allele (known as PiZZ patients), impaired degradation of the aggregated protein leads to putatively toxic accumulation of Z-AAT in the liver (toxic gain-of-function) and exerts continuous stress on the hepatocytes. Over time, this constant stress can lead to liver fibrosis, cirrhosis, and hepatocellular cancer. Currently, there is no treatment for this severe liver disease, aside from liver transplantation.

Dicerna Pharmaceuticals, Inc. is developing belcesiran, also known as DCR-A1AT, as a treatment for alpha-1 antitrypsin associated liver disease (AATLD) using an RNAi strategy to silence *SERPINA1*. This knockdown may lead to a reduction of total Z-AAT expression in the liver and, in turn, reduce the accumulation of toxic Z-AAT. Without the continuous putative toxic stimulus, the progression of AATLD in affected individuals may be halted, or potentially even reversed.

Belcesiran sodium (DCR-S1459, the drug substance for belcesiran), has been shown to significantly reduce AAT mRNA and AAT protein levels in transgenic mice and cynomolgus monkeys. Additionally, in the transgenic mouse model of AATLD, belcesiran sodium substantially reduced hepatic globules, indicating reduced accumulation of aggregated human Z-AAT protein.

The initial safety, tolerability, PK, and PD of belcesiran are being evaluated in an ongoing singleascending-dose study in healthy volunteers (DCR-A1AT-101). To date, single doses of belcesiran have been well tolerated, with no SAEs or dose-limiting toxicities (DLT) reported. Study DCR-A1AT-201 is the first study of belcesiran in adults with AATLD. The overall goals of this study are to:

- demonstrate that belcesiran is safe and well-tolerated in adult PiZZ patients with liver fibrosis;
- investigate the effect of 2 dose levels of belcesiran on reduction of Z-AAT production in the liver, reflected by a reduction in circulating Z-AAT levels; and
- evaluate the effect of belcesiran on AATLD as assessed by liver biopsy and non-invasive markers of liver disease

# **Overall Design:**

This study is a multiple dose, randomized, placebo-controlled, double-blind study to evaluate the safety, tolerability, PK, and PD of 2 belcesiran doses in adult patients with PiZZ AATLD (liver

fibrosis stage 1-4, METAVIR scoring system). Administration of the first dose of study intervention will occur on Day 1. Participants will return to the site for administration of study intervention and safety, tolerability, PK, and PD monitoring at specified time points as per the SoA through the End of Treatment (EOT) visit.

# **Intervention Groups and Duration:**

The study will be conducted in 3 separate cohorts. Participants will be randomized in a 1:1 fashion to either Cohort 1 or 2. Once Cohort 1 and 2 have enrolled, enrollment of Cohort 3 will be initiated. Randomization will be stratified based on fibrosis stage (METAVIR Score F1, F2, F3, or F4) in all cohorts.

- Participants in Cohort 1 (N=8) will be randomized 3:1 to either belcesiran 210 mg or placebo and a liver biopsy will be performed at week 24 to assess the effect of belcesiran. In addition, participants will have the option to continue treatment for an additional 72 weeks so that the total treatment duration will be 96 weeks.
- Participants in Cohort 2 (N=8) will be randomized 3:1 to either belcesiran 210 mg or placebo and a liver biopsy will be performed at week 48 to assess the effect of belcesiran. In addition, participants will have the option to continue treatment for an additional 48 weeks so that the total treatment duration will be 96 weeks.
- Participants in Cohort 3 (N=30) will be randomized 2:1:2:1 to belcesiran 210 mg, the equivalent amount of placebo for belcesiran 210 mg, belcesiran 50 mg or the equivalent amount of placebo for belcesiran 50 mg. Participants will be blinded within each dose level. Participants will have a liver biopsy performed at week 24 to assess the effect of belcesiran and thereafter continue treatment until 96 weeks of treatment have been completed.

All participants in Cohorts 1 to 3 will have the option to undergo a liver biopsy at EOT/week 96. Biopsy findings will be correlated with changes in non-invasive markers of liver disease and liver stiffness.

In all cohorts, a follow up period of 48 weeks will follow EOT. In addition, Cohorts 1 and 2 will be followed for an additional 48 weeks to inform about the duration of potential treatment effects.

#### **Study Population:**

#### **Key Inclusion Criteria:**

- 1. Male or female age 18 to 75 years inclusive, at the time of signing the ICF.
- 2. Documented diagnosis of PiZZ-type AATD, confirmed by genotyping. Historical genotyping data may be used, if available.
- 3. AATLD, with a liver fibrosis score categorized as F1, F2, F3, or F4 in the METAVIR scoring system, documented by liver biopsy during Screening.
- 4. Post-bronchodilator  $FEV_1 > 45\%$  of predicted at Screening. Participants receiving augmentation therapy on a regular basis and intending to continue augmentation therapy during the study are eligible to participate.
- 5. eGFR at Screening  $\geq 60$  mL/min normalized to 1.73 m^2 BSA.

6. Non-smokers (defined as having not smoked cigarettes daily for at least the preceding 12 months) with current non-smoking status confirmed by urine cotinine at Screening AND any previous smoking history prior to 12 months must be < 15 pack years, including use of e-cigarettes. Participants may be on nicotine replacement (patch or gum). A positive urine cotinine result due to nicotine replacement is acceptable for enrollment at the discretion of the Investigator.

# Key Exclusion Criteria:

- 1. History of chronic liver disease other than non-alcoholic fatty liver disease from any cause other than PiZZ-type AATD.
- 2. Child-Pugh Score B or C or a previous hepatic decompensation event.
- 3. History of one single severe exacerbation of underlying lung disease in the year prior to randomization.

A severe exacerbation is defined as an exacerbation that requires hospitalization or a visit to the emergency room.

4. History of rapid decline in pulmonary function, as assessed by the Investigator.

#### **Disclosure Statement**:

This is a parallel-cohort, placebo-controlled, treatment study investigating belcesiran in patients with AATLD. Participants and Investigators will be blinded to treatment. Complete details, including any Sponsor team members who are planned to be unblinded, will be presented in the Study Specific Blinding Plan.

#### Number of Participants:

Up to a total number of 16 participants will be enrolled in Cohorts 1 and 2. A total of 30 participants will be enrolled in Cohort 3.

#### **Data Safety Monitoring Committee:**

A DSMC will be convened to review safety data at predefined intervals, including at the time of a planned interim analysis, to ensure the safety of the participants in all cohorts. The timing and scope of the review meetings will be defined in the DSMC charter.

# **Objectives and Endpoints:**

Objectives			Endpoints
Prii	mary (Cohorts 1 and 2)		
1.	To evaluate the safety and tolerability of multiple doses of belcesiran in patients with AATLD	1.	The incidence and nature of TEAEs, and the change from Baseline in PFTs, 12 -lead ECGs, physical examination findings, vital signs, and clinical laboratory tests
2.	To characterize the PD of belcesiran in patients with AATLD	2.	Changes from baseline to weeks 24 (Cohort 1)/48 (Cohort 2) in serum AAT protein concentrations
Prii	mary (Cohort 3)		
1.	To characterize the PD of belcesiran in patients with AATLD	1.	Change from baseline to week 24 in serum Z-AAT protein levels
		2.	Change from baseline to week 24 in liver Z-AAT protein levels
Sec	ondary		
1.	To characterize the PK of belcesiran in the plasma of patients with AATLD	1.	PK profile of belcesiran
2.	To assess the effect of belcesiran on liver histology in patients with AATLD	2.	Change from Baseline up until week 96 in liver fibrosis
		3.	Change from Baseline up until week 96 in diastase-resistant PAS-positive AAT globules
Exp	loratory		
1.	To assess the effect of belcesiran on liver stiffness in patients with AATLD	1.	Change from Baseline up until week 96 in FibroScan ® score
2.	To assess the effect of belcesiran on liver fibrosis and/or inflammation in patients with AATLD	2.	Change from Baseline up until week 96 in ELF score
		3.	Change from Baseline up until week 96 in CK-18

\_

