- p Samples for future analysis will be collected at selected visits only if a participant has consented to future analysis.
- q Plasma samples for PK analysis will be collected predose and at 5, 15, 30, and 60 minutes and 2, 4, 6, 8, 12, and 24 hours postdose for Doses 1 and 2 only. Single samples will be collected predose for other doses and at other visits as indicated. The following windows are allowed:
  - Predose
  - 5 and 15 minutes postdose: ± 3 minutes

- 30 and 60 minutes postdose: ± 5 minutes
- 2, 4, 6, and 8 hours postdose: ± 15 minutes
- 12 and 24 hours postdose: ± 1 hour
- r Vital sign measurements will include blood pressure, pulse rate, respiratory rate, and temperature (collected per local standard of care). For Dose 1 and 2, vital sign measurements will be performed predose, at the end of injection, at 30 (± 10) and 60 (± 15) minutes, at 2 (± 30 minutes), 6 (± 30 minutes), and 24 hours (± 1 hour) postdose. At other dosing visits, vital signs will be measured predose. If multiple assessments are due at the same time, the order of priority should be ECG, vitals, PK, and then other assessments; with PK sampling being performed at the nominal time point.
- s A focused physical examination will be performed (see Section 8.2.2) for Dose 1 and 2 only, ECG will be performed predose and at 30 minutes and 6 hours postdose. For other doses, a single ECG will be performed predose. If multiple assessments are due at the same time, the order of priority should be ECG, vitals, PK, and then other assessments, with PK sampling being performed at the nominal time point.
- t At Dose 1, the required questionnaires will be performed predose. See Section 8.1.6 and 8.1.7.
- u The EOT FibroScan and MRE will be performed prior to the EOT liver biopsy. Participants must be fasting for a minimum of 3 hours prior to the FibroScan and 6 hours prior to the MRE being performed. If Screening MRE is done, it is expected that an MRE is done at EOT. If a clinical site does not have access to the required equipment or technology, MRE assessments would be optional.
- v At ET, a liver biopsy will be optional.
- w Serious AEs and treatment-emergent SAEs will be assessed until 30 days after the last day of study participation. Ongoing SAEs will be followed until resolution or until resolved with sequalae.
- x Participants should be fasting for a minimum of 8 hours prior to selected visits.

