- h A urine pregnancy test will be performed. If the result is positive, a confirmatory serum pregnancy test will be performed. Dosing should not occur unless a negative result is obtained with the confirmatory serum pregnancy test in consultation with the Sponsor.
- i Samples for complement analysis will be collected surrounding Dose 1 only. For Dose 1, samples will be collected predose, at 2 and 6 hours (± 30 minutes), and 24 hours (± 1 hour) postdose. At EOT, samples will be collected at the same time as all other sample collections.
- j The AFP sample should be collected predose.
- k Urine sample will be collected predose.
- 1 The serum AAT and CRP sample should be collected predose. Blood samples for determination of CRP will be collected at the same time as those for determination of serum AAT.
- m At all visits, the blood sample for antidrug antibodies will be collected predose.
- n Blood samples for biomarkers or fibrosis will be collected predose on dosing days.
- o Samples for future analysis will be collected at selected visits only if a participant has consented to future analysis.
- p Plasma samples for PK analysis will be collected predose and at 5, 15, 30, and 60 minutes and 2, 4, 6, 8, 12, and 24 hours postdose for Doses 1 and 2 only. Single samples will be collected predose for other doses and at other visits as indicated. The following windows are allowed:
  - Predose
  - 5 and 15minutes postdose: ± 3 minutes
- 30 and 60 minutes postdose: ± 5 minutes

• 2, 4, 6, and 8 postdose: ± 15 minutes

- 12 and 24 hours postdose: ± 1 hour
- q Vital sign measurements will include blood pressure, pulse rate, respiratory rate, and temperature (collected per local standard of care). For Dose 1 and 2, vital sign measurements will be performed predose, at the end of injection, at 30 (± 10) and 60 (± 15) minutes, at 2 (± 30 minutes), 6 (± 30 minutes), and 24 hours (± 1 hour) postdose for Dose 1 only. At other dosing visits, vital signs will be measured predose. If multiple assessments are due at the same time, the order of priority should be ECG, vitals, PK, and then other assessments; with PK sampling being performed at the nominal time point.
- r Focused physical examination (see section 8.2.2).

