### 8.2.2. Physical Examinations

A complete physical examination will be required at visits as indicated in the SoA (Section 1.3) and will include, at a minimum, assessments of the eyes, ears, nose, throat, thyroid/neck, lymph nodes, as well as cardiovascular, respiratory, gastrointestinal, musculoskeletal, dermatological, and neurological systems. Height (in cm, only at Screening), weight (in kg), and body mass index will also be measured and recorded. Height and weight should be measured without shoes.

In lieu of a complete physical examination, a focused physical examination will be performed at other visits indicated in the SoA (Section 1.3). It will include, at a minimum, assessments of the skin, lungs, cardiovascular system, and abdomen (liver and spleen).

Investigators should note any pre-existing clinical signs related to previous illnesses.

For at-home visits (whenever applicable), the home-health nurse will provide in-person support to the Investigator in assessing the participant.

Study intervention injection sites should be inspected at each visit.

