3.7 Safety Assessment

Safety and tolerability of study drug will be evaluated via the assessment of AEs, the change from Baseline in PFTs, 12-lead ECG, PE findings, vital signs, and clinical laboratory tests. All safety analyses will be performed on the Safety Population (unless specified otherwise) by actual treatment received and overall.

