3.7.5 Electrocardiograms

Standard 12-lead ECGs will be performed in the supine position after the participant has rested comfortably for 10 minutes. 12-Lead ECGs will be obtained using a machine that automatically calculates the heart rate and ventricular rate and measures RR, PR, QRS, QT, and corrected QT intervals (QTcF, Fridericia correction). For each 12-lead ECG parameter, observed values at each visit, baseline and absolute change from baseline to post-baseline visit values will be summarized using descriptive statistics.

A summary of QTc and QTcF measurements will be performed, within treatment group and time point, using counts and percentages of the number of participants with assessments that meet the following criteria: absolute QTc or QTcF > 500 msec, QTc or QTcF with a change from baseline >60 msec.

For the overall interpretation of the ECG profile, the number and percentage of participants in each category (Normal, Abnormal Not Clinically Significant, or Abnormal Clinically Significant) recorded on the CRF will be presented by visit and by treatment and overall. 12-Lead ECG data will be listed by participants.

3.7.6 *Physical Examinations (PE)*

For the overall interpretation of the PE, the number and percentage of participants in each category (Normal, Abnormal Not Clinically Significant, or Abnormal Clinically Significant) recorded on the CRF will be presented by visit and by treatment and overall. Physical examination data will be listed by participant.

3.7.7 *Other Safety Assessments*

Total complement hemolytic activity (CH50, including C3a, C5a, and Bb), serum alpha fetoprotein (AFP), coagulation parameters (aPTT, PT, and INR), antidrug antibodies, and C-reactive protein will be summarized using descriptive statistics for each visit by treatment and overall. Listings will also be provided.

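### SAP 3.7.6 tabulates physical examination categories by visit with no shift from baseline and does not separate complete from focused exams, so this component of the Cohort 1/2 safety endpoint is not delivered

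*Protocol*

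**What the plan says.** The protocol's primary endpoint for Cohorts 1 and 2 (synopsis and section 3) joins the incidence of TEAEs with change from Baseline in PFTs, ECGs, "physical examination findings, vital signs, and clinical laboratory tests". SAP 3.7 repeats it as "the change from Baseline in PFTs, 12-lead ECG, PE findings, vital signs, and clinical laboratory tests".

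The analysis is in SAP 3.7.6: "For the overall interpretation of the PE, the number and percentage of participants in each category" (Normal, Abnormal Not Clinically Significant, Abnormal Clinically Significant, as recorded on the CRF) "will be presented by visit and by treatment and overall. Physical examination data will be listed by participant". No change or shift from baseline is mentioned. The ECG paragraph just before it (SAP 3.7.5) does have one for the measured parameters: "observed values at each visit, baseline and absolute change from baseline to post-baseline visit values will be summarized using descriptive statistics". SAP 3.7.2 to 3.7.4 likewise give change from baseline for PFTs, continuous laboratory parameters and vital signs.

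Protocol 8.2.2 defines two exams. The complete exam has a long minimum list of areas. Then: "In lieu of a complete physical examination, a focused physical examination will be performed at other visits", and that exam's minimum is skin, lungs, cardiovascular system and abdomen. The schedules in Protocol 1.3 say which exam is done when. SAP 3.7.6 does not mention the distinction.

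**The concern.** There are two problems.

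First, by-visit percentages do not measure change within a participant. Improvement in some and worsening in others can leave every row the same, so the quantity named in the endpoint is not produced.

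Second, the rows are not like for like. A stable finding in, say, the musculoskeletal or neurological system is recorded at a complete exam and need not be looked for at a focused one. Read down the visits, the table can then suggest improvement where nothing changed, or understate a real rise. At stake is how one component of a primary safety endpoint is read over time, in at most 16 people, where each person moves a percentage a long way.

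**Working it through.** The plan states no rate, power or sample size for physical examination findings, so there is no figure to reproduce. The check counts exams, shows what by-visit counts can reveal, and illustrates the effect of exam type under stated assumptions.

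**1. Baseline exam type.** SAP 3.1.3 takes the last non-missing assessment before first dose. Screening and Day 1 are both complete exams in the schedules, so baseline is complete either way.

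**2. Exam counts after Day 1** (physical examination rows, Protocol 1.3):
- Cohort 1: complete on Days 57, 169, 673; focused on Days 2, 3, 15, 29, 30, 85, 113, 141, 253, 337, 421, 505, 589. Focused: 13/16 = 81%.
- Cohort 2: complete on Days 85, 169, 337, 673; focused at the other 16 exams. Focused: 16/20 = 80%.
- The cohorts differ (Cohort 1/Cohort 2) on Day 57 (complete/focused), Day 85 (focused/complete) and Day 337 (focused/complete).

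These counts rest on superscripts in the schedule tables. In the Cohort 1 footnotes the focused-exam and ECG texts run together and the later letters are out of step, so the counts hold as the tables read.

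**3. Coverage** (Protocol 8.2.2). The complete exam lists 12 areas and the focused exam 4. The 8 not in the focused minimum are eyes, ears, nose, throat, thyroid/neck, lymph nodes, musculoskeletal and neurological.

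**4. What by-visit counts can show.** With N participants, A0 abnormal at baseline and A1 abnormal later, the number newly abnormal can lie anywhere from max(0, A1 − A0) to min(A1, N − A0). For the planned 6 active participants in a cohort (3:1 of 8), with 2 abnormal at both times, that is from max(0, 0) = 0 to min(2, 4) = 2. The table is the same in every case.

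**5. Effect of exam type, illustration only.** Assume each area is abnormal with probability p, independently, with no true change. Then P(any abnormal) = 1 − (1 − p)^k, with k = 12 for complete and k = 4 for focused:
- p = 1%: 11.4% and 3.9%
- p = 2%: 21.5% and 7.8%
- p = 5%: 46.0% and 18.5%
- p = 10%: 71.8% and 34.4%

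Other assumptions give other results:
- All abnormalities in the four shared areas at 5% each: 18.5% at both, so no fall.
- Shared areas worsening from 5% to 10%, omitted areas at 2% each: 1 − 0.95^4 × 0.98^8 = 30.7% at baseline and 1 − 0.90^4 = 34.4% later. The row still rises, but by 3.7 points. Restricted to the shared areas the rise is 34.4 − 18.5 = 15.9 points.

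**6. Rows that can mix exam types.**
- *Last visit:* SAP 3.1.2 summarises all last visits for every safety assessment. The trial was stopped before planned procedures were complete (SAP 1), so last exams can be of either type.
- *Early termination:* these visits follow the Day 673 activities, which include a complete exam, and SAP 3.1.2 can reassign them to a visit where the exam is focused. A scheduled visit takes precedence if it took place, and SAP 3.1.4 limits summary tables to scheduled visits, so this route is narrow.
- *Any row pooled across cohorts* on Days 57, 85 or 337.

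**The case against.** A reader might infer that abnormality rates are bound to fall, and that the primary safety table is biased toward showing no harm. The documents do not support that:

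- Active and placebo share the exam schedule within a cohort, and the table is split by treatment. The concurrent comparison at a scheduled visit is not distorted by exam type.
- Both exam lists are minimums. A fall needs abnormalities that lie only in omitted areas and go unrecorded. The focused exam keeps skin, lungs, cardiovascular system and abdomen, which cover the organs of main safety interest.
- Complete exams recur on Day 169 in Cohort 1 and Day 337 in Cohort 2, the Week 24 and Week 48 endpoint times.
- SAP 3.1.4 and Protocol 9 say summaries are by treatment group and cohort. Pooling would depart from that general rule, although SAP 3.7.6 does not repeat it.
- New lung, skin or liver findings have other routes into the analysis: PFTs and chemistry with change from baseline, injection site reactions as AESIs, and clinically significant worsening as an adverse event (Protocol 10.3.1).
- Physical examination is one component of the endpoint, the analysis is descriptive (SAP 3.1.5), and a listing shows each participant.

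All of this stands, and it limits the consequence. It does not supply the missing analysis. Adverse events do not capture a move from Normal to Abnormal Not Clinically Significant, and a listing is not a summary of change. Protocol 9.3.1.1 asks for change from baseline where applicable; for a three-level category, a shift table is the applicable form.

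**Conclusion.** The point holds in limited form. SAP 3.7.6 does not produce the change from baseline that the endpoint and SAP 3.7 name, and it places complete and focused exams in one series of rows without marking them. Rates can therefore fall over time with no clinical change. This affects comparisons over time, last-visit rows, reassigned early-termination visits and any row pooled across cohorts. It does not affect the concurrent active-placebo comparison within a cohort.

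The size is not documented. The percentages in step 5 rest on assumed, equal and independent area rates and show direction only; under other assumptions the rate stays level or rises. The exam counts (13 of 16 and 16 of 20) rest on the schedule superscripts as they read. The change is worth making because it is cheap and supplies a result the plan already promises.

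**What to change.** Add to SAP 3.7.6:

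- A shift table of the CRF category from baseline to each complete-exam visit, by treatment and cohort: Days 57, 169 and 673 in Cohort 1; Days 85, 169, 337 and 673 in Cohort 2, once the schedule superscripts are confirmed. Give the number with both exams as the denominator, since the early stop may leave few at the later visits.
- The number of participants with a new or worsened category relative to baseline, by treatment and cohort, at those visits.
- An extension to focused visits, limited to the four shared areas, only if the CRF holds area-level results. The SAP names only an overall category, so this cannot be assumed.
- A label for exam type in every by-visit and last-visit row, including any early-termination exam reassigned to a visit, and a statement that the table is by cohort.

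The shift table uses the category already planned for tabulation, so it needs no new data. The cost is one extra table and some labelling. The downside is that fewer visits are compared with baseline; the by-visit table and listing still cover the rest.
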